6.4.1 Reporting of SAEs that are also endpoints in the study

Efficacy endpoints in the study (VOCs and acute SCD complications [TIA/ischaemic stroke, hepatic sequestration and splenic sequestration, priapism and dactylitis]) fulfilling the criteria for SAE will not be reported by AstraZeneca to health authorities to avoid unnecessary unblinding of efficacy endpoints that are also SAEs.

6.5 Overdose

An overdose is considered any dose greater than that specified in the protocol.

There is currently no known antidote to reverse the effects of ticagrelor, and ticagrelor is not expected to be dialysable. Treatment of overdose should follow local standard medical practice. The expected effect of excessive ticagrelor dosing is prolonged duration of bleeding risk associated with platelet inhibition. If bleeding occurs appropriate supportive measures should be taken.

In healthy adults, ticagrelor is well tolerated in single doses up to 900 mg. Gastrointestinal toxicity (nausea, vomiting, diarrhoea) was dose-limiting in healthy adults following ascending single doses. Other clinically meaningful adverse effects, which may occur with overdose, include dyspnoea and ventricular pauses. In the event of overdose, observe for these potential adverse effects, and consider ECG monitoring. Measure platelet inhibition to determine the extent and duration of excessive platelet inhibition.

- An overdose with associated AEs is recorded as the AE diagnosis/symptoms on the relevant AE modules in the CRF and on the Overdose CRF module.
- An overdose without associated symptoms is only reported on the Overdose CRF module.

If an overdose on an AstraZeneca study drug occurs in the course of the study, then the Investigator or other site personnel inform appropriate AstraZeneca representatives immediately, or **no later than 24 hours** of when he or she becomes aware of it.

The designated AstraZeneca representative works with the Investigator to ensure that all relevant information is provided to the AstraZeneca Patient safety data entry site.

For overdoses associated with a SAE, the standard reporting timelines apply, see Section 6.4. For overdoses not fulfilling SAE criteria, AstraZeneca will ensure that the overdose is reported to the AstraZeneca data entry site within 30 calendar days of awareness.

6.6 Pregnancy

All pregnancies and outcomes of pregnancy should be reported to AstraZeneca representatives.

6.6.1 Maternal exposure

If a patient becomes pregnant during the course of the study IP should be discontinued immediately.

Pregnancy itself is not regarded as an AE unless there is a suspicion that the IP under study may have interfered with the effectiveness of a contraceptive medication. Congenital abnormalities/birth defects and spontaneous miscarriages should be reported and handled as SAEs. Elective abortions without complications should not be handled as AEs. The outcome of all pregnancies (spontaneous miscarriage, elective termination, ectopic pregnancy, normal birth or congenital abnormality) should be followed up and documented even if the patient was discontinued from the study.

If any pregnancy occurs in the course of the study, then the Investigator or other site personnel informs the appropriate AstraZeneca representatives within 1 day, ie, immediately but **no later than 24 hours** of when he or she becomes aware of it.

The designated AstraZeneca representative works with the Investigator to ensure that all relevant information is provided to the AstraZeneca Patient safety data entry site within 1 or 5 calendar days for SAEs (see Section 6.4) and within 30 days for all other pregnancies.

The same timelines apply when outcome information is available.

The eCRF is used to report the pregnancy. The outcome of the pregnancy is reported on a separate form outside the eCRF.

6.6.2 Paternal exposure

There is no restriction on fathering children or donating sperm during the study. Pregnancies in partners are not to be reported.

6.7 Medication error

For the purposes of this clinical study a medication error is an unintended failure or mistake in the treatment process for an AstraZeneca study drug that either causes harm to the subject or has the potential to cause harm to the subject.

A medication error is not lack of efficacy of the drug, but rather a human or process related failure while the drug is in control of the study site staff or subject.

Medication error includes situations where an error:

- Occurred
- Was identified and intercepted before the patient received the drug
- Did not occur, but circumstances were recognised that could have led to an error.

Examples of events to be reported in clinical studies as medication errors:

- Drug name confusion
- Dispensing error, eg, medication prepared incorrectly, even if it was not actually given to the patient

- Drug not administered as indicated, for example, wrong route or wrong site of administration
- Drug not taken as indicated, eg, tablet dissolved in water when it should be taken as a solid tablet
- Drug not stored as instructed, eg, kept in the fridge when it should be at room temperature
- Wrong patient received the medication (excluding IXRS errors)
- Wrong drug administered to patient (excluding IXRS errors).

Examples of events that **do not** require reporting as medication errors in clinical studies:

- Errors related to or resulting from IXRS - including those which lead to 1 of the above listed events that would otherwise have been a medication error
- Patient accidentally missed drug dose(s), eg, forgot to take medication
- Accidental overdose (will be captured as an overdose)
- Patient failed to return unused medication or empty packaging
- Errors related to background and rescue medication, or standard of care medication in open-label studies, even if an AstraZeneca product.

Medication errors are not regarded as AEs but AEs may occur as a consequence of the medication error.

If a medication error occurs in the course of the study, then the Investigator or other site personnel informs the appropriate AstraZeneca representatives within 1 day, ie, immediately but **no later than 24 hours** of when he or she becomes aware of it.

The designated AstraZeneca representative works with the Investigator to ensure that all relevant information is completed within 1 or 5 calendar days if there is an SAE associated with the medication error (see Section 6.4) and within 30 days for all other medication errors.

6.8 Management of IP-related toxicities

See Section 3.9.

7. INVESTIGATIONAL PRODUCT AND OTHER TREATMENTS

7.1 Identity of investigational product(s)

Investigational product	Dosage form and strength	Manufacturer
Ticagrelor 15 mg tablet	Oral, plain, round, biconvex, white/off-white, uncoated, 15 mg	AstraZeneca
Placebo for ticagrelor 15 mg tablet	Oral, plain, round, biconvex, white/off-white, uncoated, containing no active ingredient	AstraZeneca

Ticagrelor tablets of 15 mg and its matching placebo (approximately 6 mm in diameter) will be packed in high-density polyethylene bottles containing 100 tablets. Subsequent intervals between dispensing visits should not be more than 100 days.

7.2 Dose and treatment regimens

Allocation of IP bottles will be managed via the IXRS and at Visit 2, first dose of the IP will be administered at the clinic by site staff. Subsequent doses should be taken morning and evening, at approximately 12-hour intervals. The IP can be taken with or without food.

7.2.1 Treatment during double-blind randomisation period

Randomisation to twice daily double-blind treatment with ticagrelor or placebo will occur at Visit 2 via the IXRS. Eligible patients will be randomly assigned to 1 of 2 treatment regimens, based on body weight at Visit 2:

- ≥ 12 to ≤ 24 kg body weight: 15 mg - 1 tablet of ticagrelor 15mg or 1 tablet of placebo to match ticagrelor 15 mg twice daily
- > 24 to ≤ 48 kg body weight: 30 mg - 2 tablets of ticagrelor 15mg or 2 tablets of placebo to match ticagrelor 15mg twice daily
- > 48 kg body weight: 45 mg - 3 tablets of ticagrelor 15mg or 3 tablets of placebo to match ticagrelor 15mg twice daily

At Visit 2, the first dose of IP will be administered at the clinic by site staff as soon as possible after randomisation and after all baseline assessments have been completed. Subsequent doses should be taken morning and evening, at approximately 12-hour intervals. Missed doses of ticagrelor or placebo blinded IP should not be compensated (ie, if a dose is missed the next regularly scheduled dose should be taken and should not be doubled).

The study drug will be administered orally either swallowed whole or dispersed in water, other suitable liquids or vehicles based on age and/or ability to swallow study drugs. Refer to handling instructions for further details.

7.2.2 Dose increase during study

For any patient having a weight gain during the study period clearly exceeding the upper weight limit of the band (≥ 27 kg and ≥ 54 kg, respectively), the dose will need to be increased according to the next weight band.

In case of a dose increase:

- IXRS will generate correct dose based on body weight range entered
- Stop date for the old dose and start date for the new dose should be recorded in the eCRF
- The patient should return all unused IP and empty bottles and new IP bottles should be dispensed
- PK and PD samples should be taken at the following visit after the adjusted dose has been dispensed, see Sections 5.4 and 5.5.

7.3 Labelling

Labels will be prepared in accordance with Good Manufacturing Practice (GMP) and local regulatory guidelines. The labels will fulfil GMP Annex 13 requirements for labelling. Label text will be translated into local language.

7.4 Storage

All study drugs should be kept in a secure place under appropriate storage conditions. The IP label on the bottle specifies the appropriate storage.

7.5 Compliance

The administration of IP (ticagrelor or placebo) should be recorded in the appropriate sections of the eCRF.

Each time IP is dispensed, compliance will be reinforced. The caregiver will be asked to bring all unused IP and empty bottles to the study site at each on-site visit. When IP is returned, compliance will be assessed based upon an interview with the caregiver and a count of the tablets returned.

7.6 Accountability

The IP provided for this study will be used only as directed in the Clinical Study Protocol.

The study site staff will account for all IPs dispensed to and returned from the patient.

The caregiver will be asked to bring all unused IP and empty bottles to the study site at each on-site visit. The Investigator or delegate will enter the amount of returned tablets in the eCRF.

Study site personnel or the AstraZeneca delegated monitor will account for all IPs received at the site, empty bottles, unused study drugs and for appropriate destruction, according to local procedures at an authorised site. Certificates of delivery, destruction and return must be signed by an AstraZeneca representative.

7.7 Concomitant medication and other treatments

See [Appendix G](#) for a complete list of restricted medications. All concomitant medications and any changes during the study should be recorded by the Investigator in the eCRF.

Use of anti-platelet aggregation drugs like ADP receptor blockers (eg, cangrelor, clopidogrel, prasugrel, ticlopidine) or aspirin, or phosphodiesterase inhibitors (eg, dipyridamole and cilostazol) is not allowed in the study.

Treatment with oral or parenteral anticoagulants (except for heparins for flushing of catheters) is not allowed in the study. Chronic non-steroidal anti-inflammatory agents (requiring treatment >3 days/week) is not allowed in the study (see exclusion criteria in [Section 3.2](#)).

CYP3A inhibitors

Concomitant use of strong inhibitors of CYP3A (eg, boceprevir, clarithromycin, conivaptan, indinavir, itraconazole, ketoconazole, lopinavir/ritonavir, mibefradil, nefazodone, nelfinavir, posaconazole, ritonavir, saquinavir, telaprevir, telithromycin, voriconazole) is not allowed. When macrolide antibiotics is indicated azithromycin is allowed.

CYP3A substrates or inducers

Co-administration of CYP3A substrates with a narrow therapeutic index is not allowed. Co-administration of strong inducers of CYP3A (eg, rifampin/rifampicin, rifabutin, phenytoin, carbamazepine, phenobarbital, avasimibe, St. John's wort) is not allowed.

P-glycoprotein interactions

Ticagrelor is a weak inhibitor of P-glycoprotein (P-gp), a drug efflux transporter. Digoxin is a substrate of P-gp and concurrent treatment with ticagrelor modestly increases digoxin levels. If the patient is receiving digoxin, levels should be monitored closely following initiation of IP and with any change in IP.

7.7.1 Blood transfusions

If a patient requires any blood transfusion during the study, this information will be captured in the eCRF.

7.7.2 Other concomitant treatment

If a patient is treated with hydroxyurea, the weight-adjusted dose must be stable for 3 months before enrolment.

Other medication other than that described above, which is considered necessary for the patient's safety and well-being, like L-glutamine may be given at the discretion of the Investigator and recorded in the appropriate sections of the eCRF. The entry must include the dose, regimen, route, indication and dates of use.

Patients may not participate in any other interventional drug study for at least 30 days prior to starting this study and may not participate in any other interventional drug study throughout the study period.

7.8 Post study access to study treatment (Not applicable)

8. STATISTICAL ANALYSES BY ASTRAZENECA OR DELEGATE

Statistical analyses are summarised below. Further details will be provided in the Statistical Analysis Plan (SAP).

8.1 Statistical considerations

Statistical analyses will be performed by IQVIA under the direction of Biometrics & Information Sciences, AstraZeneca using SAS[®] version 9.2 or higher and, where appropriate, additional validated software.

IQVIA will finalise the SAP according to any required regulatory timelines but before review of any potential treatment revealing data is undertaken (this includes Blind Deliverable Reviews and Data Monitoring Committee reviews).

8.2 Sample size estimate

The number of VOCs is assumed to have a negative binomial distribution with shape parameter 0.8. The mean number of crises per year is assumed to be 2.0 in the placebo group with reduction of 50% in the ticagrelor group. Patients will be randomised to 1:1 ratio and with minimum follow-up of 12 months and average follow-up of 18 months, 154 patients provide about 90% power for a 2-sided test of the mean number of crises for ticagrelor versus placebo, at significance level 5%. Allowing for dropouts, the sample size is increased to 182. The calculations were based on simulation with 5,000 repetitions.

Scenarios and simulations were evaluated to assess the risk with shorter and longer mean follow-up time. To ensure that the study is adequately powered the recruitment rate will be monitored and the sample size may be adjusted to a maximum of 200 patients. With a mean follow-up time of 13 month, 200 patients will provide 90% power to detect a reduction of 50% in the ticagrelor group.

8.3 Definitions of analysis sets

8.3.1 Full analysis set

All randomised patients, regardless of treatment received, will be included in the Full Analysis Set. The primary statistical analysis of the efficacy of ticagrelor will be carried out on the Full Analysis Set. Patients will be analysed according to their randomised IP.

8.3.2 Safety analysis set

All patients who receive at least 1 single dose of randomised IP, ticagrelor or placebo, and for whom any postdose data are available, will be included in the safety analysis set. Erroneously treated patients (eg, those randomised to treatment A but actually given treatment B) will be accounted for in the actual treatment group, where actual treatment is defined as: ticagrelor if a patient receives at least 1 dose of ticagrelor, otherwise actual treatment is placebo.

8.3.3 PK analysis set

All patients who receive at least 1 dose of IP and provide at least 1 post dose analysable plasma sample for PK analysis will be included in the PK analysis set.

Patients with major protocol deviations including changes to the procedures that may impact the quality of the data, or any circumstances that can alter the evaluation of the PK may be excluded from the PK analysis set.

8.3.4 PD analysis set

All patients who have receive at least 1 dose of IP and provide at least 1 postdose analysable sample for PD analysis will be included in the PD analysis set.

Patients with major protocol deviations including changes to the procedures that may impact the quality of the data, or any circumstances that can alter the evaluation of the PD may be excluded from the PD analysis set.

8.4 Outcome measure for analyses

See Section 2 for outcome measures.

8.5 Methods for statistical analyses

In general;

- Ticagrelor data will be pooled and analysed irrespective of dose.
- Safety, plasma concentrations of ticagrelor and active metabolite, HRQL variables will be presented using descriptive statistics and graphed as appropriate.
- Categorical variables will be summarised in frequency tables (number of patients and percentage), by treatment group.
- Continuous variables will be presented with descriptive statistics (n, arithmetic mean, standard deviation [SD], median, min, max), within treatment group. If appropriate, geometric mean and coefficient of variation (CV) will be used instead of arithmetic mean and SD, with CV (%) calculated as:

$$100 \cdot \sqrt{\left(\exp(s^2) - 1\right)} \text{ where } s \text{ is the SD of the data on a log scale.}$$

- Data will also be presented in individual patient listings.
- Baseline values will be the closest observation prior to and including the randomisation visit.

8.5.1 Analysis of the primary variable

The primary analysis will be based on the intent-to-treat principle. Ticagrelor data will be pooled and analysed irrespective of dose.

The number of VOCs will be analysed using negative binomial regression. Any VOC event with an onset date within 7 days from a prior event onset date will not be counted as a new

episode. The response variable is the number of VOCs experienced by a patient over the treatment period. Patient follow-up time (log-transformed) will be included as an offset in the linear predictor to adjust for patients having different exposure times. Additional covariates to be adjusted for in the linear predictor will be treatment group (placebo as reference group) and baseline hydroxyurea therapy (Yes/No). The treatment effect will be tested at a 5% significance level.

If the negative binomial distribution is not appropriate, a Wilcoxon rank sum test will be used. As the Wilcoxon rank sum test cannot be adjusted for the patients follow-up time, sensitivity analyses will be performed to ensure robustness of the results.

The primary analysis (under the treatment policy estimand) includes all data until patients withdraw from the study regardless of if they discontinue from randomised treatment. The primary analysis uses the negative binomial regression model with logarithm of the observation period as an offset term and assumes that missing data is missing at random. Hence, the model assumes that the frequency-of-events during an unobserved period is the same as the frequency estimated using observed data.

To examine the sensitivity of the results and the robustness of this assumption analyses will be performed using controlled multiple imputation method. For this method, an underlying negative binomial stochastic process for the number of VOCs is assumed and post study withdrawal counts will be imputed based on the observed number of events prior to the withdrawal.

The following, but not limited to, missing data analysis will be performed:

- Missing counts in each arm are imputed assuming the expected event rate within that arm. This method corresponds closely to the original model and the results are expected to correspond closely to the primary analysis. This analysis is included to allow for comparison with the partial-DRMI method.
- Multiple imputation based on dropout reason (partial-DRMI); Missing counts will be imputed differently depending on the reason for dropout; meaning that counts for patients in the ticagrelor arm who withdraw consent for a potential treatment related reason are imputed based on the expected event rate in the placebo arm, whereas the remaining patients who have withdrawn consent are imputed assuming missing at random. Potential treatment related reasons include but are not limited to AEs, deaths and development of study specified reasons.

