3.10.2 Withdrawal of the informed consent

Patients are free to withdraw from the study at any time (ie, permanent discontinuation of IP and study schedule assessments), without prejudice to further treatment.

Withdrawal of consent from the study must be documented by the Investigator in the patient medical records and recorded in the electronic case report form (eCRF) as well as in the Informed Consent Form (ICF). The reason for permanent discontinuation of IP, the date of the last dose of the IP, reason for withdrawal and the presence of any AEs must be documented in the eCRF. The Investigator will follow-up AEs outside of the clinical study. The patient will return the electronic device (eDevice).

If a patient withdraws from participation in the study, then his/her enrolment/randomisation code cannot be reused. Withdrawn patients will not be replaced after randomisation.

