Appendix E Accounting for Missing Data

Accounting for missing data for recurrent events (VOC event rate endpoint)

In this study some patients dropping out of the study potentially leads to unobserved events. The amount of missing data is minimised in this study as patients are encouraged to remain in the study after premature discontinuation of double-blind randomised study treatment and complete visits according to the protocol schedule of assessments.

This section describes the plan to account for missing data in the sensitivity analyses to assess the robustness of the treatment effect under different underlying assumptions to account for missing data.

Missing data descriptions

Tabular summaries for the percentage of patients by the reason for premature discontinuation of double-blind randomised study treatment as well as for early withdrawal from the study will be presented by double-blind randomised treatment group to describe why patients prematurely discontinue from double-blind randomised treatment or withdraw prematurely from the study.

Primary analysis under the Treatment Policy Estimands using the Missing at Random (MAR) assumption

The primary analysis is under the treatment policy estimand which allows for differences in outcomes over the entire defined double-blind randomised treatment period to reflect the effect of initially assigned randomised study treatment as well as if subsequent alternative treatments for SCD are taken. This primary analysis includes all data until patients withdraw from the study regardless of whether they prematurely discontinue from double-blind randomised study treatment. The primary analysis uses the negative binomial regression model with (logarithm of) the observation period as an offset term and assumes that missing data is missing at random (MAR) and is a direct likelihood approach (DL).

Sensitivity analyses under the Treatment Policy Estimands using both MAR and MNAR assumptions

To examine the sensitivity of the results of the primary analysis to departures from the underlying assumptions, additional analyses will be performed using controlled multiple imputation (MI) methods which allow for different underlying assumptions to be used. As with the primary analysis the sensitivity analyses include all data until patients withdraw from the study regardless of whether they prematurely discontinue from double-blind randomised study treatment.

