- 2 Partial Dropout Reason-based Multiple Imputation (pDRMI): Missing counts will be imputed differently depending on the reason for dropout; counts for patients in the Ticagrelor groups who dropped out for a study treatment-related reasons are imputed based on the expected VOC event rate in the placebo treatment group, whereas the remaining patients who have dropped out are imputed assuming MAR. Study treatment-related reasons may include (1) AEs, (2) Death and (3) Development of study-specified reasons.
- 3 Dropout Reason-based Multiple Imputation (DRMI): As for pDRMI with study treatment-related reasons and including "severe non-compliance with the protocol".

A review of each patient who withdraws from the study will be carried out prior to database lock and routine study unblinding. The review will include assessment of the reason for

discontinuation of double-blind randomised study treatment for those patients who discontinued the double-blind randomised study treatment and then withdrew from the study and free text for when the reason for withdrawal or discontinuation of double-blind randomised study treatment is “subject decision” or “other”. Based on this review the default assumptions for pDRMI and DRMI may be changed. A list of these patients and the assumptions made under pDRMI and DRMI will be documented prior to database lock and routine study unblinding.

A summary of reasons for patients withdrawing from the study and the corresponding treatment group used to calculate the imputation VOC event rate under MAR, pDRMI, and DRMI is given in [Table 5](#).

Table 5 Reasons for patients withdrawing from the study and the corresponding treatment group used to calculate the imputation VOC event rate under MAR, pDRMI, and DRMI

Reason for withdrawal ^a	MAR	pDRMI	DRMI
Death	Ticagrelor	Placebo	Placebo
Severe non-compliance to protocol	Ticagrelor	Based on review of important protocol deviations prior to study unblinding	Based on review of important protocol deviations prior to study unblinding
Patient lost to follow-up	Ticagrelor	Based on review prior to study unblinding	Based on review prior to study unblinding
Withdrawal by patient	Ticagrelor	Based on review prior to study unblinding	Based on review prior to study unblinding
Other ^b	Ticagrelor	Based on review prior to study unblinding	Based on review prior to study unblinding

^aAll patients withdrawing from placebo have VOC event rate imputed using the placebo treatment group rate.

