^bAll patients withdrawing for a COVID-19 related reason, regardless of which category of reason is collected for them, will be reviewed prior to study unblinding

In addition, a tipping point analysis will be performed (if appropriate, ie, the primary efficacy was a favourable result) using the same model as above and where:

- Missing counts for a patient will be imputed, according to the rate of the double-blind randomised treatment group that the patient belongs to multiplied by a factor delta (δ).
- A series of analyses will be performed with a range of increasing deltas for the two treatment groups (δ_P and δ_T for placebo and ticagrelor groups respectively) so that one can assess at which point the study conclusions would change from favourable to unfavourable; ie, to identify a tipping point.

In this assessment, the ticagrelor group is assumed to worsen after withdrawal. Therefore, deltas will be increased starting from 1 in increments of 0.025, until a favourable primary efficacy result is no longer favourable. If statistical significance is maintained among the matrix of possible δ combinations, the comparison is deemed robust to missing data.

Together with the primary analysis the sensitivity analyses are considered to cover the range from realistic to plausible worst-case assumptions about missing data. The MAR multiple imputation approach is expected to correspond closely to the primary analysis and is included to allow for comparisons with MNAR assumptions using the same multiple imputation methodology.

The pDRMI/DRMI approach was selected as the most conservative approach because placebo patients are potentially receiving standard of care and are not expected to change to a substantially more effective treatment after withdrawing from study or double-blind randomised study treatment. For patients receiving ticagrelor who withdraw from the study due to study treatment-related reasons it is assumed that at worst they would be on the standard of care treatment ie, the placebo group.

On-treatment Analyses (Efficacy and Effectiveness estimands)

In addition, primary and sensitivity analyses described previously, two alternative estimands will be estimated using only the initial randomised study treatment data:

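### The primary analysis is labelled treatment policy but carries withdrawn ticagrelor patients at their arm's observed VOC rate, and no unconditional planned analysis puts them all at an off-drug rate

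*Protocol*

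**What the plan says.** SAP Appendix E defines the target: "The primary analysis is under the treatment policy estimand which allows for differences in outcomes over the entire defined double-blind randomised treatment period". The model is a negative binomial regression with log follow-up time as offset. It uses all data up to study withdrawal, including data collected after the drug was stopped. For time after withdrawal, Protocol 8.5.1 states that "the model assumes that the frequency-of-events during an unobserved period is the same as the frequency estimated using observed data", which is a missing-at-random (MAR) assumption.

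Protocol 3.10.2 says what withdrawal means: "Patients are free to withdraw from the study at any time (ie, permanent discontinuation of IP and study schedule assessments". The heading of Protocol 7.8 reads "Post study access to study treatment (Not applicable".

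Appendix E plans controlled multiple imputation. Under pDRMI, ticagrelor patients who leave for treatment-related reasons are imputed at the placebo rate, "whereas the remaining patients who have dropped out are imputed assuming MAR". DRMI adds severe non-compliance to those reasons. Appendix E then says: "The pDRMI/DRMI approach was selected as the most conservative approach". It also describes the whole set as reaching plausible worst-case assumptions. A tipping-point analysis follows only if the primary result is favourable. SAP 4.2.6.3 makes the missing-data analyses depend on how much data are missing, whereas Protocol 8.5.1 commits to them.

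**The concern.** A treatment-policy estimand asks for the VOC rate over the whole period, whatever treatment was actually taken. A ticagrelor patient who withdraws consent is off the drug from then on. Giving that time the arm's observed rate answers a different question: what would have happened had the patient carried on as observed. The observed rate contains on-drug time plus any off-drug time from patients who stopped the drug but stayed in follow-up.

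The SAP itself supplies the premise that the effect may be lost. It argues that ticagrelor patients who leave for treatment-related reasons would at worst resemble the placebo group, and it defines a separate estimand with loss of effect after stopping ticagrelor. It does not explain why the effect should persist in a patient who leaves for another reason.

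At stake is the size of the reported rate ratio relative to its stated estimand, and whether a reader can see how far it depends on this assumption.

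**Working it through.** **Inputs from the documents (Protocol 8.2 and 1.2.2).** Placebo rate 2.0 per year; 50% reduction, so ticagrelor 1.0 per year; shape 0.8; 1:1 allocation; follow-up 12 to 24 months, mean 18, uniform enrolment.

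**Reproducing the plan's figure.** The plan states: "154 patients provide about 90% power for a 2-sided test of the mean number of crises for ticagrelor versus placebo, at significance level 5"%. Read shape 0.8 as dispersion k = 1/0.8 = 1.25. Per arm, Var(log rate) = 1/Σ[μ/(1 + kμ)], with μ = rate × time and time uniform on 1 to 2 years.
- Placebo: the mean of μ/(1 + kμ) is 0.6275; × 77 = 48.3; variance 0.0207.
- Ticagrelor: the mean is 0.5172; × 77 = 39.8; variance 0.0251.
- SE = √0.0458 = 0.214. Then 0.693/0.214 − 1.96 = 1.28, so power is 90.0%.

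The plan's figure reproduces.

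**Implied dropout.** No dropout rate is given, only "Allowing for dropouts, the sample size is increased to 182". From this, 1 − 154/182 = 28/182 = 15.4%. (154/0.85 = 181.2, which also rounds up to 182, so 15% may have been meant.)

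**Assumptions not in the documents.** The share of follow-up lost per withdrawn patient: 50%, range 25% to 100%. The share of lost time spent at the placebo rate: 100%, range 25% to 100%.

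**Formula.** f = dropout × share of follow-up lost × share of lost time at the placebo rate.
RR over the whole period = [1.0(1 − f) + 2.0f]/2.0 = 0.5(1 − f) + f.
Gap = ln(RR) − ln(0.5), as a percentage of 0.693.

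**Central case.** f = 0.154 × 0.5 × 1 = 0.077. RR = 0.5 × 0.923 + 0.077 = 0.538. The log RR is −0.619 against −0.693, so the gap is 0.074, and 0.074/0.693 = 10.7%. Large simulations of the same model gave 10.8% and 10.9%.

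| Dropout | Follow-up lost | Lost time at placebo rate | f | RR | Gap |
|---|---|---|---|---|---|
| 15.4% | 50% | 100% | 7.7% | 0.538 | 10.7% |
| 15.4% | 25% | 100% | 3.8% | 0.519 | 5.4% |
| 15.4% | 75% | 100% | 11.5% | 0.558 | 15.8% |
| 15.4% | 100% | 100% | 15.4% | 0.577 | 20.6% |
| 15.4% | 50% | 50% | 3.8% | 0.519 | 5.4% |
| 15.4% | 50% | 25% | 1.9% | 0.510 | 2.7% |
| 5% | 50% | 100% | 2.5% | 0.5125 | 3.6% |
| 10% | 50% | 100% | 5.0% | 0.525 | 7.0% |
| 25% | 50% | 100% | 12.5% | 0.5625 | 17.0% |

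The range of about 3% to 21% at 15.4% dropout comes from moving one assumption at a time away from the central case. With both at 25% the gap is 1.4%.

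**Retained off-drug data.** If a further 10% to 15.4% of patients stop the drug but stay in follow-up, the simulated gap is 9.7% to 9.4%.

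**No drug effect.** With equal rates, RR = 1(1 − f) + 1f = 1, so the gap is zero.

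**What the planned analyses leave.** If half of the withdrawals count as treatment-related (an assumption), pDRMI gives RR 0.519 in the central case against 0.538. The remaining gap is ln(0.538/0.519)/0.693, about 5%. For the other reasons, the pDRMI text and Table 7 use the ticagrelor rate, subject to review. Table 5 fixes the placebo rate only for death and sends every other listed reason to review before unblinding.

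**The case against.** The plan hides nothing. It states the MAR assumption, tests it with pDRMI, DRMI and a tipping point, and adds on-treatment estimands. The protocol's list of missing-data analyses is expressly open-ended. Patients who stop the drug are asked to stay in follow-up, so the observed rate is not purely on-drug. Table 5 leaves most withdrawal reasons to review before unblinding, so more patients may be imputed at the placebo rate than the pDRMI text suggests. After a favourable result, the tipping point either passes through the scenario at issue (δ of 2.0/1.0 = 2 for ticagrelor and 1 for placebo, at the planned rates) or tips sooner and shows fragility. Patients lost to follow-up may also hold dispensed tablets for a time.

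All of this stands, and it limits the point. It does not close the gap: the review may or may not assign these patients to the placebo rate, and the tipping point yields a boundary, only after a favourable result.

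A second objection also stands. Imputing everyone at the placebo rate is itself an assumption. The treatment-policy estimand includes alternative SCD treatments taken later, so a reader should not take the placebo-rate figure as the true treatment-policy value.

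Finally, SAP 3.1.4.1 now ends the study at the date when investigators were told to stop treatment. The 12 to 24 months used above are the planned follow-up. Earlier truncation may leave less unobserved time; the documents do not say how much.

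**Conclusion.** The mismatch between label and assumption is real. The primary model gives withdrawn ticagrelor patients, who are off drug by the protocol's definition, the arm's observed rate. If the drug works and its effect is lost off drug, the error favours ticagrelor.

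The size is conditional. It is about 11% of the assumed log rate ratio if 15.4% withdraw, half of their follow-up is lost and all return at once to the placebo rate. At that dropout it is about 3% to 21%, and it is zero if rates do not rise off drug.

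A reader might infer two stronger claims. One is that the plan overstates the effect by 11% as a matter of fact. The documents give no dropout rate, withdrawal timing or off-drug VOC rate, so they do not support it. The other is that the test is biased towards a false positive. On this mechanism there is no bias under the null; only the size of a true effect is at issue.

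The statement that pDRMI/DRMI is the most conservative approach is wrong as written. When ticagrelor has the lower rate, imputing all ticagrelor withdrawals at the placebo rate is more conservative.

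**What to change.** Keep the primary model unchanged. Then:

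1. Add to SAP Appendix E and Table 7 one pre-specified treatment-policy sensitivity analysis. Impute every ticagrelor patient who withdraws from the study, whatever the reason, at the placebo-arm rate from the withdrawal date. Run it whatever the primary result and show it in the forest plot beside the primary. Describe it as a reference-based assumption. It needs no classification of reasons, so it does not depend on the review in Table 5.
2. Delete the statement that pDRMI/DRMI is the most conservative approach.
3. State plainly that the primary analysis assumes withdrawn ticagrelor patients keep the arm's observed rate.

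The cost is SAP wording and one more run of imputation code already planned. The downside is a little more analysis work and an added estimate that would be slightly less favourable to ticagrelor if the drug works.
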